## **8.6 Adjustment of Dose and/or Treatment Schedule**

Dose adjustments for PLT count reduction must be made in accordance with [Table 2](#) (above).

Other adjustments, including dose interruptions, and/or decreasing the dose will be allowed for safety or tolerability after consultation with the Sponsor Medical Monitor or designee.

Dose adjustments should not occur unless absolutely necessary prior to Week 25.

## **8.7 Discontinuation of Study Drug Administration**

Reasons for permanent discontinuation of Study Drug administration are:

- The patient experiences an AE that necessitates permanent discontinuation of Study Drug

- At the discretion of the Investigator due to a safety concern
- At the patient's request due to an adverse event
- The patient develops laboratory test abnormalities that meet any of the stopping rules listed in Section 8.5
- The patient becomes pregnant. Report the pregnancy according to instructions in Section 9.5.4
- Reasons not related to an AE
  - Patient request to stop Study Drug but continue study participation
  - The patient withdraws consent for study participation
  - Investigator decision (e.g., non-compliant patient)
  - Sponsor decision

The reason for discontinuation of Study Drug must be recorded in the eCRF and source documentation. If the Investigator decides that discontinuation of Study Drug is warranted, the Investigator should make every effort to contact the Sponsor or TIMI Hotline prior to discontinuation of Study Drug.

Patients who had Study Drug administration discontinued for any reason other than full withdrawal of consent for study participation should continue their participation in the study, attending visits and procedures as per Section 8.7.1, if possible, and providing survival status by the end of the trial. If the patient declines or is unable to attend study visits, the Investigator should clarify what type of follow-up the patient is agreeable to: in person, by phone/mail, through family/friends, via correspondence/communication with other physicians, and/or from review of the medical records, and as allowed per local regulations. Wherever possible these patients should continue to be followed up via the agreed means to collect information on AE, concomitant medications and survival status. At the very least, the patient's status at the end of the Treatment Period should be ascertained and documented wherever possible. The agreed means of follow-up will be documented in the patient records and notified to the Sponsor.

#### **8.7.1 Follow-up Visits for Early Termination from Treatment Period or Post-Treatment Follow-up Period**

If a patient discontinues early from the Treatment Period, treatment early termination (Tx-ET) visit assessments should be performed 4 weeks from the last dose of Study Drug, and patients should start the 13-week Post-Treatment Follow-up Period to collect the study assessments in accordance with the Schedule of Procedures in Appendix A. Patients should also be strongly encouraged to attend remaining landmark visits at Weeks 25 and 27, as well as at Weeks 51 and 53 (calculated based on the time elapsed since Day 1) to collect fasting lipid panels and conduct safety assessments in accordance with Appendix A. Depending on the day of discontinuation, follow-up visits and landmark visits may overlap and can be combined.

Any patient who chooses to discontinue early from the Post-Treatment Follow-up Period should be strongly encouraged to complete safety procedures and observations in accordance with Appendix A. If the patient declines or is unable to participate in the above, final post-treatment

early termination (Post-Tx ET) assessments should be performed at the time of withdrawal in accordance with [Appendix A](#).

## **8.8 Withdrawal of Patients from the Study Procedures**

A participant may withdraw from the study at any time at his/her own request. Patients should be encouraged to complete the early termination study procedures and observations at the time of withdrawal ([Appendix A](#)). All efforts will be made to complete and report the observations as thoroughly as possible up to the date of withdrawal. All information, including the reason for withdrawal from study, must be recorded in the eCRF.

Full withdrawal of consent: Any patient who provides full withdrawal of consent to participate in the study will be removed from further treatment and study observation immediately upon the date of request.

If a participant withdraws consent from the study, he/she may request destruction of any remaining samples taken and not tested, and the Investigator must document any such requests in the site study records and notify the Sponsor accordingly.

If the participant withdraws consent for disclosure of future information, no further evaluations should be performed, and no additional data should be collected. The Sponsor may retain and continue to use any data collected before such withdrawal of consent. In participants who request to prematurely stop Study Drug and study-related procedures, collection of adverse events and clinical endpoints will continue as permitted by local laws and regulations, unless the participant requests otherwise.

Lack of completion of all or any of the withdrawal/early termination procedures will not be viewed as protocol deviations so long as the participant's safety was preserved.

Publicly available information should be used to determine vital status (whether the participant is alive or dead) as permitted by local law.

### **8.8.1 Lost to Follow-up**

To prevent participants being lost to follow-up, their contact details, including next of kin contacts, should be collected initially and updated regularly by the site staff or representative. The Investigator should educate the participant on the importance of contact with the Investigator throughout the study.

Repeated attempts will be made to locate and obtain pertinent medical information for participants who are initially lost to follow-up. A participant will be classified as lost to follow-up only if he/she has failed to return for the required study visits and his/her vital status remains unknown at the end of the study despite multiple attempts to contact him/her via telephone, fax, email, certified letter, or through patient locator agencies (if allowed by national regulation). Where permissible by local law, the Informed Consent Document will include language to grant the option to employ outside companies to assist in obtaining updated contact information or ascertainment of vital status of lost participants using publicly available source.

## **8.9 Concomitant Therapy and Procedures**

The use of concomitant therapies or procedures defined below must be recorded on the patient's eCRF. Adverse events related to administration of these therapies or procedures must also be documented on the appropriate eCRF.

### **8.9.1 Concomitant Therapy**

A concomitant therapy is any non-protocol specified drug or substance (including OTC medications, herbal medications and vitamin supplements) administered from the time the patient has signed the informed consent at Screening to the end of the Post-Treatment Follow-up Period.

#### **Allowed Concomitant Therapy**

Any medications deemed necessary by the Investigator are allowed except those listed in the disallowed concomitant therapy.

#### **Disallowed Concomitant Therapy**

Study patients are prohibited from receiving other experimental agents during the study. This includes marketed agents at experimental dosages that are being tested for the treatment of hypertriglyceridemia.

Patients should consult with the Investigator or designee prior to initiating any new medication, including non-prescription or herbal compounds or any other non-drug therapy. If a disallowed concomitant therapy is administered, the study Investigator must discuss with the Medical Monitor / TIMI whether Study Drug may continue. Regardless of the decision regarding Study Drug continuation, all other study procedures and follow-up should continue as described in the protocol.

### **8.9.2 Concomitant Procedures**

A concomitant procedure is any therapeutic intervention (e.g., surgery/biopsy, physical therapy) or diagnostic assessment (e.g., blood gas measurement, bacterial cultures) performed between Screening and the end of the Post-Treatment Follow-up Period.

#### **Disallowed Concomitant Procedures**

Plasma apheresis is not allowed during the study.

## **8.10 Treatment Compliance**

At each applicable dosing visit, patients may be administered study drug by a delegated study staff member. The study drug administration and compliance will be documented as per the protocol, Study Drug Manual, and captured in the electronic data capture system. If study drug is administered by a home healthcare professional, source documentation will be completed and provided to the site to document the details of study drug administration. If study drug is self-administered, after appropriate training of patient and/or caregiver, site staff will record the study drug administration details via contact with the patient.

## 9 SERIOUS AND NON-SERIOUS ADVERSE EVENT REPORTING

### 9.1 Sponsor Review of Safety Information

Safety information will be collected, reviewed, and evaluated by the Sponsor or designee in accordance with the applicable Ionis and/or designee SOPs throughout the conduct of the clinical trial.

### 9.2 Regulatory Reporting Requirements

The Sponsor or designee is responsible for regulatory submissions and reporting to the Investigators of SAEs including SUSARs per the ICH guidelines E2A and ICH GCP. Country-specific regulatory requirements will be followed in accordance with local country regulations and guidelines.

Institutional Review Boards (IRB)/Independent Ethics Committees (IEC) will be notified of any SAE according to applicable regulations. The DSMB will be notified of any SAE as specified in the DSMB charter.

In addition to the Investigator's assessment of relatedness, the Sponsor or designee will evaluate the available information and perform an independent assessment of all reported SAEs and determine if there is a reasonable possibility that the Study Drug (ISIS 678354 or placebo) is causally related to a reported SAE.

The Sponsor or designee will evaluate the available information for all reported SAEs and decide if there is a reasonable possibility that the Study Drug (olezarsen or placebo) caused the SAE and, therefore, meets the definition of a SUSAR.

Appropriate personnel at the Sponsor or designee will unblind SUSARs for the purpose of regulatory reporting. The Sponsor or designee will submit SUSARs to Regulatory Agencies in blinded or unblinded fashion in accordance with EC Clinical trials Directive 2001/20/EC or as per national regulatory requirements in participating countries.

### 9.3 Definitions

#### 9.3.1 Adverse Event

An adverse event (AE) can be any unfavorable and unintended sign (including an abnormal laboratory finding, for example), symptom, or disease temporally associated with the use of medicinal (investigational) product, whether or not the AE is considered related to the medicinal (investigational) product.

An adverse event can therefore be any of the following:

- Any unfavorable and unintended sign (including an abnormal laboratory finding), symptom, or disease temporally associated with the use of a medicinal product, whether or not considered related to the medicinal product
- Any new disease or exacerbation of an existing disease (a worsening in the character, frequency, or severity of a known condition)

- Recurrence of an intermittent medical condition (e.g., headache) not present at Baseline
- Any deterioration in a laboratory value or other clinical test (e.g., ECG, X-ray) that is associated with symptoms or leads to a change in study treatment or concomitant treatment or discontinuation from Study Drug
- Adverse events that are related to a protocol-mandated intervention, including those that occur prior to assignment of study treatment (e.g., screening invasive procedures such as biopsies)

### **9.3.2 Adverse Drug Reaction and Suspected Unexpected Adverse Drug Reaction**

#### **Adverse Drug Reaction (ADR)**

In the *pre-approval* clinical experience with a new medicinal product or its new usages, particularly as the therapeutic dose(s) may not have been established, ADR is defined as follows:

All noxious and unintended responses to a medicinal product related to any dose should be considered ADR.

The phrase "responses to a medicinal product" means that a causal relationship between the medicinal product and the adverse event has been determined by the Sponsor as at least a reasonable possibility, i.e., the relationship cannot be ruled out.

#### **Suspected Unexpected Adverse Drug Reaction**

A suspected unexpected ADR is any ADR, the nature or severity of which is not consistent with the applicable product information, e.g., Investigator's Brochure for an unapproved medicinal (investigational) product.

A suspected adverse reaction implies a lesser degree of certainty about causality than an adverse reaction.

### **9.3.3 Serious Adverse Event (SAE)**

A SAE is any adverse event that in the view of either the Investigator or Sponsor, meets any of the following criteria:

- Results in death
- Is life threatening: that is, poses an immediate risk of death at the time of the event  
Note: An AE or suspected adverse reaction is considered "life-threatening" if, in the view of either the Investigator or Sponsor, its occurrence places the patient at immediate risk of death. It does not include an AE or suspected adverse reaction that, had it occurred in a more severe form, might have caused death
- Requires inpatient hospitalization or prolongation of existing hospitalization
- Results in a persistent or significant incapacity or substantial disruption of the ability to conduct normal life functions
- Results in a congenital anomaly or birth defect in the offspring of the patient (whether the patient is male or female)

- Important medical events that may not result in death, are not life-threatening, or do not require hospitalization may also be considered serious when, based upon appropriate medical judgment, they may jeopardize the patient and may require medical or surgical intervention to prevent 1 of the outcomes listed in this definition. Examples of such medical events include allergic bronchospasm requiring intensive treatment in an emergency room (ER) or at home, blood dyscrasias or convulsions that do not result in inpatient hospitalization, the development of drug dependency or drug abuse, or spontaneous abortion/miscarriage

The terms "severe" and "serious" are not synonymous. Severity refers to the intensity of an adverse event (e.g., rated as mild, moderate, or severe, or according to National Cancer Institute Common Terminology Criteria for Adverse Events [NCI CTCAE]; OR Toxicity Grading Scale for Healthy Adult and Adolescent Volunteers Enrolled in Preventive Vaccine Clinical Trials; the event itself may be of relatively minor medical significance (such as severe headache without any further findings).

Severity and seriousness need to be independently assessed for each adverse event recorded on the eCRF.

#### **9.3.4 Adverse Event of Special Interest**

An adverse event of special interest (AESI), including both serious or non-serious events is one of scientific and medical concern specific to the Sponsor's product or program, for which ongoing monitoring and rapid communication by the Investigator to the Sponsor may be appropriate.

Adverse events of special interest are required to be reported by the Investigator to the Sponsor following the same requirements as for SAE reporting (Section 9.4.1).

For the purpose of this study there are 2 AESIs:

1. Severe reductions in PLT count  $< 50,000/\text{mm}^3$  accompanied by a MB event or CRNMB event, or PLT count of  $< 25,000/\text{mm}^3$  independent of a MB or CRNMB event.
2. Requirement of any use of medications (such as antihistamines, acetaminophen, non-steroidal anti-inflammatory drugs [NSAIDs], corticosteroids, etc.) as pre-treatment to avoid a hypersensitivity reaction or recurrence of a previous hypersensitivity reaction.

### **9.4 Monitoring and Recording Adverse Events**

Any pre-existing conditions or signs and/or symptoms present in a patient prior to the start of the study (i.e., before informed consent) should be recorded as Medical History and not recorded as AEs unless the pre-existing condition worsened. The Investigator should always group signs and symptoms into a single term that constitutes a **single unifying diagnosis** if possible. Before a diagnosis is confirmed, all symptoms should be reported as separate AEs.

#### **9.4.1 Serious Adverse Events**

In the interest of patient safety, and in order to fulfill regulatory requirements, all SAEs and AESIs (regardless of their relationship to Study Drug) should be reported to the Sponsor or designee immediately, without undue delay, but no later than within 24 hours of the Study

Center's first knowledge of the event. The collection of SAEs will begin after the patient signs the informed consent form and stop at the end of the patient's Follow-up Period. SAEs should be captured and reported electronically within Electronic Data Capture System (EDC). The SAE reporting instruction, including the fax number and email address can be found in the Investigator site file for the study.

Detailed information should be actively sought and included on electronic Adverse Event Forms in EDC as soon as additional information becomes available. All SAEs will be followed until resolution. SAEs that remain ongoing past the patient's last protocol-specified follow-up visit will be evaluated by the Investigator and Sponsor. If the Investigator and Sponsor agree the patient's condition is unlikely to resolve, the Investigator and Sponsor will determine the follow-up requirement.

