#### **9.4.2 Non-Serious Adverse Events**

The recording of non-serious AEs will begin after the patient signs the informed consent form and will stop at the end of the patient's Follow-up Period. The Investigator will monitor each patient closely and record all observed or volunteered AEs on the Adverse Event Case Report Form.

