- K Recommended time points for qualified site personnel to reinforce compliance to diet/ life-style modifications and alcohol restrictions ([Appendix E](#))
- L Study Drug can be administered at home by patient or caregiver after receiving appropriate training
- M Assessments and procedures to be conducted by either the Study Center or by a Home Healthcare service (if available and permitted by local regulations) as arranged by the Study Center personnel. Physical Exam will be Body Assessment if conducted by a Home Healthcare professional
- N Landmark visit. For early termination landmark (ET-L) visits: Week 25 is ET-L1, Week 27 is ET-L2, Week 51 is ET-L3, and Week 53 is ET-L4
- O Weeks/days from end of treatment. End of treatment is defined as 1 dosing interval (4 weeks) post-last dose

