All AEs and SAEs that occur during the study that are consistent with an event of acute pancreatitis will be adjudicated by a blinded, independent committee according to the Atlanta classification of acute pancreatitis and as outlined in the PAC. These events will be categorized by the various criteria to be one of the following: 1) documented pancreatitis, 2) probable pancreatitis, 3) possible pancreatitis, 4) unable to adjudicate, and 5) no diagnosis of acute pancreatitis. For the purposes of data analysis, events that are documented, probable or possible are to be considered adjudicated acute pancreatitis. A listing will be provided to display each adjudicator's and the final adjudication committee's classification results for each event. The adjudicated acute pancreatitis event rates will be compared between pooled olezarsen treatment and placebo group using a Negative Binomial regression model or Poisson regression model with the treatment group and natural log transformed baseline fasting TG as the factors, and number of adjudicated acute pancreatitis events in 5 years prior to the enrollment as a covariate. The logarithm of time in year that each patient observed during the Treatment Period will be used as an offset variable.

From the models, the mean rate and SEM for each treatment group as well as the mean rate ratio relative to the placebo group and corresponding 95% CIs will be estimated. The p-value of Wald-based chi-square test will also be reported.

Week 53 is defined as Day 379 (scheduled visit day plus a 14-day window) or the last contact date within the study, whichever is earlier. If patients have intercurrent event(s) before Week 53, the Treatment Policy strategy will be implemented, the pancreatitis events occurred post intercurrent events will continue to be collected. All adjudicated pancreatitis events including those post the intercurrent events will be included in the analysis. For patients who discontinued the treatment early and were lost to follow-up before Week 53, the pancreatitis event rate will be adjusted by the length of observation time in the analysis model.

The sample SAS code for the Negative Binomial regression model can be found below:

```

/*****
/* Note*/
/* logbase      = log transformed baseline TG                               */
/* trtpn = treatment group: 0=pooled placebo, 1=olezarsen 80 mg or 50 mg      */
/* numevent = number of adjudicated acute pancreatitis events                */

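### Protocol 9.4.1 and 9.4.2 end AE and SAE collection with the Follow-up Period, which contradicts the sections and SAP rates that carry early stoppers on to Week 53

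*Combined protocol and SAP*

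**What the plan says.** **The stop rule.** Protocol 9.4.1: "The collection of SAEs will begin after the patient signs the informed consent form and stop at the end of the patient's Follow-up Period". Protocol 9.4.2 says that recording of non-serious events "will stop at the end of the patient's Follow-up Period".

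**When Follow-up ends for an early stopper.** Under protocol 8.7.1, after the early-termination visit 4 weeks from the last dose, "patients should start the 13-week Post-Treatment Follow-up Period to collect the study assessments". The Appendix A legend fixes the starting point: "End of treatment is defined as 1 dosing interval (4 weeks) post-last dose".

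**What continues after that.**
- Section 8.7.1 says the same patients should be "strongly encouraged to attend remaining landmark visits at Weeks 25 and 27, as well as at Weeks 51 and 53", for lipids and for safety assessments under Appendix A.
- The Adverse Events row of Appendix A is marked at all four of those visits (ET-L1 to ET-L4).
- Section 8.7 asks for adverse event information, by whatever means is agreed, from patients who cannot or will not attend.
- Section 8.8 keeps adverse event and endpoint collection going after a patient stops both drug and procedures, unless the patient objects.

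**What the SAP counts.**
- For the pancreatitis rate, SAP 4.9.3.5 says that "the pancreatitis events occurred post intercurrent events will continue to be collected" and closes observation at Day 379 "or the last contact date within the study, whichever is earlier".
- SAP 4.2.1 runs exposure-adjusted time for event-free patients to last participation or data cutoff.
- SAP 4.11.3.1 divides MACE events by total follow-up time.

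**The concern.** The explicit stop sits in the section that carries the 24-hour SAE reporting duty, so it is the text a site is likely to apply when deciding whether an event must still be reported. For an early stopper it can fall months before Week 53. Pancreatitis and MACE adjudication both start from reported AEs and SAEs (protocol 9.4.3.7, SAP 4.1.3), so an event that is not reported is not adjudicated. If the patient later attends a landmark visit, or is otherwise in contact, the SAP counts the intervening time as observed.

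At stake are the two pancreatitis comparisons in the ranked sequence (SAP 4.9.1.5), the exploratory MACE rate and the exposure-adjusted safety rates. The pancreatitis analysis follows a treatment-policy strategy, so it depends on complete information from patients off drug. Those are the patients for whom the instructions conflict.

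**Working it through.** **1. The plan's own figure.** SAP 4.9.3.5 closes the pancreatitis window at Day 379. Week 53 is Day 365, and 365 + 14 = 379. The midpoint of Day 365 and the first follow-up visit (365 + 28 = 393) is also 379. The figure reproduces.

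**2. End of collection under a literal reading.** Inputs: 28 days from last dose to end of treatment (Appendix A legend) and 91 days of Follow-up (Appendix A).

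Follow-up end = last-dose day + 28 + 91 = last-dose day + 119.

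Gap = window end minus Follow-up end, with a floor of 0.

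| Last dose (Week / Day) | Follow-up ends | Gap to Day 365 | Gap to Day 379 |
|---|---|---|---|
| 1 / 1 | 120 | 245 | 259 |
| 5 / 29 | 148 | 217 | 231 |
| 9 / 57 | 176 | 189 | 203 |
| 13 / 85 | 204 | 161 | 175 |
| 17 / 113 | 232 | 133 | 147 |
| 21 / 141 | 260 | 105 | 119 |
| 25 / 169 | 288 | 77 | 91 |
| 29 / 197 | 316 | 49 | 63 |
| 33 / 225 | 344 | 21 | 35 |
| 37 / 253 | 372 | 0 | 7 |
| 41 / 281 | 400 | 0 | 0 |
| 45 / 309 | 428 | 0 | 0 |

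A gap to Day 365 arises only when the last dose is at Week 33 or earlier. Against Day 379, Week 37 adds 7 days.

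**3. Share of risk time, upper bound.** Assumptions, none of them from the documents: last doses spread evenly over the 12 rows; every early stopper followed to the window end; nothing collected in the gap. The mean gap is 1197/12 = 99.75 days (Day 365) or 1330/12 = 110.83 days (Day 379).

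Share = early-stopping proportion × mean gap / window length.

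- 5%: 0.05 × 99.75/365 = 1.4%; 0.05 × 110.83/379 = 1.5%.
- 10%: 2.7%; 2.9%.
- 20%: 5.5%; 5.9%.

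If only half of early stoppers are followed to the window end and the rest leave at Follow-up end, the shares are about 0.7%, 1.4-1.5% and 2.8-3.0%. The even spread matters: if all of a 20% group stopped after the first dose, the share would be 0.20 × 245/365 = 13.4%, or 0.20 × 259/379 = 13.7%.

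**4. Effect on a rate ratio.** Take 20% early stopping in one arm and 5% in the other (assumed), equal true rates, and the same upper-bound conditions. The Day 379 gap fraction is 110.83/379 = 0.292. The ratio reads (1 - 0.20 × 0.292)/(1 - 0.05 × 0.292) = 0.942/0.985 = 0.96, in favour of the arm with more stopping.

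**5. Scheduled contact inside the gap.** After a last dose at Week 1, Follow-up ends on Day 120 and the landmark visits fall on Days 169, 183, 351 and 365. The uncontacted stretches are 169 - 120 = 49 days and 351 - 183 = 168 days. Adverse events are reviewed at each of those visits, but a site applying 9.4.1 and 9.4.2 would have no duty to report what it learned there.

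**The case against.** The strongest reply is that the plan does provide for later collection. Appendix A marks adverse events at every ET-L visit, 8.7 and 8.8 continue collection away from the clinic, SAP 4.9.3.5 states that pancreatitis events after discontinuation are gathered and counted, and the treatment-emergent definition in SAP 4.10.2.1 has no end date. Nor does risk time run to Week 53 for everyone: landmark attendance is only encouraged, and the SAP cuts time at last contact or last participation. Time therefore accrues mainly for patients still in touch, from whom other sections ask for adverse event information. Deaths have a separate route through survival and vital status.

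All of this stands. A reader of 9.4.1 and 9.4.2 alone might infer that later events go unrecorded and that the whole gap is counted as event-free. The documents do not support that. With a last dose at Week 9, for example, landmark visits on Days 183, 351 and 365 all fall inside the 189-day gap, each with adverse events marked. Nor do the documents show that early stopping differs by arm, so step 4 is an illustration only.

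The reply does not remove the contradiction. The later provisions show intent, yet the only sentences that state when collection ends say something else, and 8.7 applies only where possible. The fallback for too few pancreatitis events (SAP 4.9.3.5) does not help either, because an unreported event is missing from a proportion as well as from a rate.

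There is also a definitional way out: protocol 6.1.2 ends the Treatment Period 4 weeks after the last dose, and on that reading pancreatitis time would close before Follow-up does. SAP 4.9.3.5 does not use that reading.

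**Conclusion.** Wrong as written: an internal contradiction. Protocol 9.4.1 and 9.4.2 give one end for AE and SAE collection; 8.7, 8.7.1, 8.8, Appendix A and SAP 4.9.3.5 assume a later one for patients who stop drug early. Events between the two may be missed, depending on which text a site follows, while the rate denominators can keep running.

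The size is modest. The 5%, 10% and 20% early-stopping rates are assumptions. The 20% matches the dropout figure in protocol 10.2, but dropping out of the study is not the same as stopping drug and staying in. The percentages are upper bounds given evenly spread last doses, and the true effect is smaller wherever sites follow Appendix A and 8.7. They refer to the 365- or 379-day window. For the on-study safety rates, where a completer's time runs to Day 337 + 119 = 456, the shares would be somewhat lower. The pancreatitis comparisons are the last two in the hierarchy and MACE is exploratory. The reasons to correct it are complete safety reporting off drug and numerators that match their denominators.

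**What to change.** **Protocol 9.4.1 and 9.4.2:** change the stop to the later of (a) the end of the patient's Follow-up Period and (b) the patient's last study visit or contact, including the Week 53 landmark visit (ET-L4). This matches 8.7, 8.7.1, 8.8 and Appendix A.

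**SAP 4.2.1, 4.9.3.5 and 4.11.3.1:** end each patient's time at risk no later than the last date on which adverse event information was obtained. At the same time, state that the pancreatitis window in 4.9.3.5 departs from the Treatment Period defined in protocol 6.1.2, or align the two.

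**Cost:** two sentences in the protocol and one censoring rule in the SAP. Adverse event review at the landmark visits is already scheduled. The downside is slightly more AE and SAE reporting for patients off drug. With collection extended this way, the gap in the table is 0 days for every early stopper who remains in contact.
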